The efficacy of SWORD Phoenix has already been demonstrated in two previous feasibility studies conducted at Hospital da Prelada, Porto, Portugal, between December 2016 and March 2018 (Clinical trial IDs: NCT03047252 and NCT03045549). These were two parallel-group studies, comparing the clinical evolution of patients submitted to an 8-week rehabilitation program after THA or TKA, divided into two distinct groups: the experimental group, which performed a home-based rehabilitation program using SWORD Phoenix, and the control group, which was also engaged in a home-based rehabilitation program, but with conventional physiotherapy instead. Geographical location was used as the allocation criterion, with patients living within the city's administrative limits allocated to the conventional physiotherapy group and patients living outside the city's administrative limits allocated to the experimental group. Results from the experimental group were superior to those from the conventional physiotherapy group in all outcome measures, and adverse effects rates were similar in both groups. The main results of the TKA study were already published ²⁸, and the main results of the THA study are in publication route.

More recently, a new version of the system was developed, where the possibility to execute bilateral exercises was added, focusing not only on the rehabilitation of the affected limb, but also on muscular reinforcement of the contralateral limb. As such,

a new clinical study was designed, aiming at exploring the clinical impact of this update on the therapeutic program (bilateral).

The present study is a single-center, prospective, single-arm, historical control study, designed to evaluate the clinical outcomes of a bilateral home-based rehabilitation program using **SWORD Phoenix®**. The clinical outcomes will be compared to those of the above-mentioned feasibility studies. The investigation hypothesis is that the clinical outcomes of the bilateral exercise program will be superior to those of the unilateral exercise program.

2. Study Outcomes

The aim of the studies is to evaluate the clinical impact of a home-based bilateral rehabilitation program after THA or TKA, using **SWORD Phoenix®**.

a) Primary outcome

The primary outcome will be the change in patient performance compared to the baseline, measured through the TUG.

b) Secondary outcomes

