- The change in patient reported outcomes, measured by HOOS and KOOS scales, as compared to baseline evaluation
- The change in the maximum amplitude of joints movements, as compared to baseline evaluation

3. Sample size estimate

Sample size estimation calculations were performed taking into consideration the primary outcome measure - Timed up and Go (TUG) test score. Calculations were based on the baseline TUG distribution of the participants in the two previous feasibility studies (total n=131; mean 18,00 seconds; sd=6,3) and on a Minimal Clinical Significant Change of 2.27 seconds as reported by Yuksel *et al.*²⁹.

Considering a power of 80%, a two-sided 0.05 significance level and an allocation rate of 2:1, 216 patients (144 in this study; 72 historical control) would be necessary to detect a 2.27 seconds difference against the historical control.

4. Inclusion criteria

- a) Patients over 18 years old
- b) Clinical and imaging evidence of hip/knee osteoarthritis
- c) Indication for total hip or knee replacement according to the patient's orthopedic surgeon
- d) Ability to walk unaided, with unilateral or bilateral support
- e) Availability of a caregiver to assist the patient after surgery

5. Exclusion criteria

- a) Patients admitted for revision of total hip/knee replacement
- b) Contralateral hip or knee osteoarthritis severely limiting patient mobility and ability to comply with a rehabilitation program
- c) Aphasia, dementia or psychiatric comorbidity interfering with the communication or compliance to the rehabilitation process
- d) Respiratory, cardiac, metabolic or other condition incompatible with at least 30 minutes of light to moderate physical activity
- e) Major medical complications occurring after surgery that prevent the discharge of the patient within 10 days after the surgery
- f) Other medical and/or surgical complications that prevent the patient from complying with a rehabilitation program
- g) Blind and/or illiterate patients
- h) Patients residing outside a 30km radius from the investigation center

6. Methods for identifying and recruiting patients

All patients admitted for total hip or knee replacement during the study period will

be screened for inclusion and exclusion criteria.

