c) Range of motion of the hip and knee

Hip and knee range of motion will be assessed based in three distinct positions: lying, sitting and standing. The system used in the study is a validated medical device for joint angle measurement. Therefore, knee range of motion will be measured automatically by the system.

In this study, the active range of motion will be measured through the following movements:

| Knee: | Hip: |
|------------------------|-----------------------------|
| Lying knee flexion | Lying hip flexion |
| Sitting knee flexion | Lying hip abduction |
| Standing knee flexion | Standing hip flexion |
| Sitting knee extension | Standing hip abduction |
| | Standing hip hyperextension |

To assess range of motion, the investigator will need to:

- 1) Create a patient profile in the Portal
- 2) Prescribe one set of each exercise, with 5 repetitions
- 3) Ask the patient to perform the session through the App, executing each repetition to the best of his ability
- 4) After the session, login to the Portal, go to the session's results and click on detailed results for each exercise. Record the flexion or extension angle of the best repetition for each exercise in the patient file.

10. Patient assessment

Patients will be assessed at baseline (pre-operatively) (A1), upon discharge (A2), at 4 weeks after rehabilitation program initiation (A3), and at the end of it (A4).

Assessments will be performed within a time window of 5-working-days, previous or ahead of the day the assessment was scheduled for.

Baseline assessment (A1)

Participant characterization will consist of:

- Demographics (gender, age at enrollment);
- Educational level (years at school);
- Diagnosis and affected side
- Date of surgery

- Height, weight, body Mass Index
- Comorbidities
 - Smoking
 - Diabetes
 - Cardiac disease
 - Respiratory disease
 - Hypertension
 - Stroke
 - Renal Disease
 - Bleeding disorders
 - Previous hip/knee replacement
 - American Society of Anesthesiologists physical status classification score of 3 or 4⁴²

b) HOOS/KOOS score

c) Timed Up and Go (TUG) test score

d) Hip and knee active range of motion

Assessment upon discharge (A2)

Patients will be reevaluated immediately upon hospital discharge, and the following parameters will be registered:

- Surgery date
- Operative time
- Type of prosthesis
- Adverse effects before discharge

Subsequent assessments (A3 e A4)

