Patients will be reassessed at 4 and 8 weeks after rehabilitation program initiation, collecting the following data:

- TUG score
- HOOS / KOOS score
- Maximum range of motion of the affected joint

11. Intervention

Upon hospital discharge, all participants will have immediate access to home-based rehabilitation therapy.

The rehabilitation program will be carried out at home, using **SWORD Phoenix®**. Patients will be instructed to engage on their rehabilitation sessions daily, but will not be excluded from the study in case this periodicity is not respected.

The rehabilitation programs proposed are presented in **Tables 1 to 4**.

Table 1: Hip replacement rehabilitation protocol - Stage 1 (weeks 0-5)

| Stage 1 (weeks 0-4) | |
|--|--|
| Objectives | Precautions |
| Decrease pain and swelling | Avoid hip internal rotation and hip adduction beyond neutral |
| Restore range of motion | Avoid hip flexion above 90° |
| Strengthen hip flexors and abductors | Ice pack application after each session and throughout the day as needed |
| Restore full load capacity on both legs | |
| Intervention | |
| Open kinetic chain exercises without added resistance | |
| Lying: 
 - Bilateral Hip Flexion (1x20-24 reps) - Operated Limb Hip Flexion (1x12-14 reps) - Bilateral Hip Abduction (1x20-24 reps) - Operated Limb Hip abduction (1x20-24 reps) - Bilateral Knee flexion (1x20-24 reps) - Operated Limb Knee Flexion (1x12-14) | |
| Standing (initially with support) 
 - Bilateral Hip Flexion (1x20-24 reps) - Operated Limb Hip Flexion (1x12-14 reps) - Bilateral Hip Abduction (1x20-24 reps) - Operated Limb Hip abduction (1x12-14 reps) - Bilateral Knee flexion (1x20-24 reps) - Operated Limb Knee Flexion (1x12-14 reps) - Bilateral Hip Flexion with Knee Flexion (1x20-24) - Operated Limb Hip flexion with knee flexion (1x12-14 reps) - Bilateral Hip hyperextension (1x20-24 reps) - Operated Limb Hip Hyperextension (1x12-14 reps) | |
| Closed kinetic chain exercises | |
| 
 - Bridge (2x12-14) - Squats (2x12-14 reps) | |
| Note 1: adjust sets, reps and total session duration according to patient tolerance (based on patient performance and on the pain and fatigue scores attributed by the patient at the end of each session) | |

Note 2: aim for at least 30 minutes in total

Note 3: recommend two daily sessions as soon as tolerated

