Extraordinary visits or phone call may be performed in case of necessity. Whenever it happens, these events will be recorded on patient's file (date, occurrence, duration)

13. Safety and adverse events

Patient safety will be ensured at all times during the sessions, and will be evaluated through pain and fatigue scores (graduated from 0 to 10) collected at the end of each session. These will be presented to the patient using the mobile App and will be available for remote monitoring by their physical therapist. In case of excessive pain or fatigue, patients will be contacted by their physical therapist to ascertain the cause and change prescription. Patients will also be asked to report any other adverse events to their physical therapist by telephone, and these will be registered on the patient's file (date of the event, date of resolution - if applicable, resolution

state, gravity).

14.Risks and Benefits to Participants

All participant will benefit from therapeutic rehabilitation immediately upon hospital discharge. Thus, the access to rehabilitation care is assured, which will likely translate into potential benefits for the patient. Patients will engage in a home-based rehabilitation program through **SWORD Phoenix®**, according to the latest treatment guidelines and following the clinician's recommendations. A physiotherapist will be allocated to each patient, guaranteeing a continuous follow up and home visits whenever necessary. Since the system will be used in line with its certified therapeutic indications, there will be no added risk or inconvenient to the user. In fact, the rate of adverse events reported on previous clinical trials was identical to that reported with conventional physiotherapy. Hence, participants are not exposed to any added risk, being able instead to directly benefit from a breakthrough technology, that allows a real and immediate measure of their performance, increasing their motivation and maximizing rehabilitation outcomes even further.

15.Results analysis

Per-protocol and intention-to-treat analysis will be applied to evaluate the study outcomes. Participants with an adhesion rate below 43% (corresponding to less than 3 sessions per week) will not be considered in the per-protocol analysis.

Intervention's impact on primary and secondary outcomes will be performed considering the variables evolution when comparing basal assessment and assessment at 8 weeks.

16.Confidentiality of Personal Data

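### Days from surgery to the primary TUG are neither aligned nor adjusted for, so any timing difference from the historical cohort would be read as a programme effect

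*Combined protocol and SAP*

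**What the plan says.** All references are to the combined protocol and SAP.

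- **Outcome (Section 2).** "The primary outcome will be the change in patient performance compared to the baseline, measured through the TUG". Section 10 places the baseline assessment (A1) before the operation.
- **Visit clock (Section 10).** "Patients will be reassessed at 4 and 8 weeks after rehabilitation program initiation, collecting the following data". These visits are A3 and A4.
- **Window (Section 10).** "Assessments will be performed within a time window of 5-working-days, previous or ahead of the day the assessment was scheduled for".
- **Start of rehabilitation (Sections 11 and 12).** "Upon hospital discharge, all participants will have immediate access to home-based rehabilitation therapy". Section 12 has a physiotherapist make an initial home visit to teach use of the system and prescribe the exercises. It sets no time limit for that visit after discharge.
- **Hospital stay (Section 5, item e).** One exclusion reads "Major medical complications occurring after surgery that prevent the discharge of the patient within 10 days after the surgery". It concerns major medical complications and is not a general limit on stay.
- **Comparator (introduction).** Outcomes are compared with those of two feasibility studies run from December 2016 to March 2018, with an 8-week home programme after hip or knee replacement. Their surgery-to-start intervals and visit windows are not given.
- **Analysis (Section 15).** Impact is assessed "considering the variables evolution when comparing basal assessment and assessment at 8 weeks". No model, covariate or alignment on time since surgery is named, although Section 10 records the surgery date.

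**The concern.** The change in TUG from a pre-operative baseline to A4 combines the effect of the operation, spontaneous recovery and the rehabilitation programme. How much recovery it contains depends on how long after surgery the patient is tested. That interval is the sum of hospital stay, delay to starting rehabilitation, 8 weeks, and the deviation of the visit from its due date. The plan fixes only the 8 weeks.

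In a randomised trial the other components would balance on average. Here the comparison is with patients treated in an earlier period. If stay, start delay or visit timing changed between the periods, the two cohorts would be measured at different points on the recovery curve under the same 8-week label. A later-measured new cohort would look better with no programme effect, and an earlier-measured one would look worse. A larger sample does not remove this error.

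There is some reason to check. The introduction says that historical patients using the system were those living outside the city limits, while the new study excludes patients living more than 30 km from the centre. The catchments may therefore differ, and starting depends on a home visit.

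**Working it through.** **Inputs from the plan.** Visits at 28 and 56 days from rehabilitation start; window of 5 working days, about 7 calendar days, each way (Section 10). SD 6.3 s, target difference 2.27 s, 144 new and 72 historical patients, two-sided 0.05 (Section 3). The SD is that of baseline TUG, not of change, and is used here because it is the only one given.

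**Assumed inputs.** Hospital stay 1-10 days; start delay 0, 7 or 21 days; TUG improvement around A4 of 0.1-1.0 s per week. The 21 days borrows the 3 weeks after discharge from the consensus recommendation in the introduction, which is not a study rule.

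**The plan's own figure.** With the stated inputs (two-sided, 2:1) the usual formula gives 91 + 182 = 273 patients, not 216; 72 + 144 = 216 matches a one-sided 0.05 test. That is a separate matter. It matters here only because two-sided power at 72 and 144 is 70.4%, the reference value below.

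**1. Spread in days since surgery.** Day of A4 = stay + start delay + 56 ± 7.

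- Window alone: 2 × 7 = 14 days.
- Stay 1-10, no delay: 1 + 56 − 7 = day 50 to 10 + 56 + 7 = day 73, a span of 23 days.
- Delay up to 7 days: day 50 to 10 + 7 + 56 + 7 = day 80, a span of 30 days.
- Delay up to 21 days: day 50 to 10 + 21 + 56 + 7 = day 94, a span of 44 days.

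These are ranges for individual patients, not differences between cohort means.

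**2. Same timing in both cohorts.** Treat each component as uniform. With no delay, the SD of timing is √((14² + 9²)/12)/7 = 0.69 weeks; with delay up to 21 days it is √((14² + 9² + 21²)/12)/7 = 1.11 weeks. In the worst case (1.0 s per week, 21 days) the TUG SD rises from 6.30 to √(6.3² + 1.11²) = 6.40, and power falls from 70.4% to 69.1%.

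**3. A difference in mean timing.** Bias = slope × mean difference. The standard error is 6.3 × √(1/72 + 1/144) = 0.909 s. With no true effect, the two-sided false-positive rate is Φ(bias/0.909 − 1.96) + Φ(−bias/0.909 − 1.96).

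| Mean difference | Bias (0.1-1.0 s per week) | Share of 2.27 s | False-positive rate |
|---|---|---|---|
| 0.5 week | 0.05-0.5 s | 2-22% | 5.0-8.5% |
| 1 week | 0.1-1.0 s | 4-44% | 5.1-19.6% |
| 2 weeks | 0.2-2.0 s | 9-88% | 5.6-59.5% |

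If the new cohort is measured 1 week earlier instead, and the true effect is 2.27 s, power falls from 70.4% to between 66.5% and 28.7%.

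**The case against.** The strongest reply is that bias needs a systematic timing difference, and the documents show none. A reader might infer that recovery time is already mixed into the comparison. The documents do not support that: they are silent on historical timing, so a difference is possible but undocumented, and its direction is unknown. The slope and the size of the shift are assumptions too. If stay alone had to produce a 1-week difference, the cohort means would have to lie 7 days apart within an assumed range of 9 days. Only a difference in start delay or visit timing would make larger shifts easier to reach. The statement of immediate access at discharge also counts against long delays, although it sets no deadline for the first home visit. All of this stands and limits the point to a conditional one.

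A reader might also infer that the wide window adds material noise within the cohort. Step 2 shows that it does not.

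A third tempting reading is that A4 should be allowed only on or after its due date, because Section 10 places it at the end of the programme and the window lets it fall about a week early. A symmetric window around a nominal 8-week visit is an ordinary scheduling choice. A forward-only window would also apply to the new cohort alone. If historical visits used a symmetric window, which is not known, and visits spread evenly, the mean A4 would move about 3.5 days later. At 0.1-1.0 s per week that is 0.05-0.5 s in favour of the bilateral programme, which would create the very bias at issue.

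Finally, counting from rehabilitation start is a sound way to equalise programme exposure, and Section 15 names no covariates at all, so time since surgery is one instance of an unadjusted historical comparison. Both are fair. Neither removes the need to report and adjust for a variable that the new study can already derive.

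**Conclusion.** The point holds in conditional form. The visit anchor, the window, the pre-operative baseline, the non-randomised comparator and the absence of any planned adjustment are all in the text. Days from surgery to the primary TUG can vary by 14 days from the window alone, and by about 3 weeks if stay ranges over an assumed 1-10 days. Whether the cohorts differ on average cannot be told from the documents. If they do, a 1-week mean difference would distort the comparison by 0.1-1.0 s, or 4-44% of the 2.27 s target, for or against the programme, under the assumed slope. If they do not, the consequence is negligible. The visit schedule itself needs no change; the gap is in the analysis plan.

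**What to change.** Keep the rehabilitation-start anchor and the symmetric window. In Section 15, pre-specify that:

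1. days from surgery to A3 and to A4 are derived from recorded dates and their distribution is reported for each cohort;
2. days since surgery at assessment is a covariate in the bilateral-versus-historical comparison of TUG, at least as a pre-specified sensitivity analysis, and likewise for HOOS/KOOS and range of motion;
3. if the historical dates cannot be obtained, this is stated as a limitation of the comparison.

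The cost is a few sentences and one covariate. In the new cohort the surgery date is recorded (Section 10) and the questionnaire sheets are dated at each assessment (Section 9). The real cost lies in the historical data: surgery and visit dates are needed for those patients, and nothing in the documents confirms that they are available. If the two distributions turn out to overlap little, the adjusted estimate will rest on extrapolation and should be described that way.

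### Section 15 evaluates impact only as change from the pre-operative baseline to week 8 and does not carry through the comparison with the earlier unilateral cohort that the hypothesis requires

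*Combined protocol and SAP*

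**What the plan says.** The text before section 2 describes a single-arm study with a historical control and states: "The clinical outcomes will be compared to those of the above-mentioned feasibility studies". It continues: "The investigation hypothesis is that the clinical outcomes of the bilateral exercise program will be superior to those of the unilateral exercise program".

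Section 2 makes change in TUG from baseline the primary outcome. Section 3 gives "216 patients (144 in this study; 72 historical control") as the number that "would be necessary to detect a 2.27 seconds difference against the historical control", at 80% power, two-sided 0.05 and 2:1 allocation. The SD comes from the "baseline TUG distribution of the participants in the two previous feasibility studies (total n=131; mean 18,00 seconds; sd=6,3").

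Section 10 places the baseline before surgery and the last assessment at the end of the programme, 8 weeks after it starts.

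Section 15 contains three things: intention-to-treat and per-protocol analyses will both be done; participants below 43% adherence leave the per-protocol set; and the intervention's "impact on primary and secondary outcomes will be performed considering the variables evolution when comparing basal assessment and assessment at 8 weeks".

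The earlier studies had two groups: one using SWORD Phoenix, "and the control group, which was also engaged in a home-based rehabilitation program, but with conventional physiotherapy instead". The protocol reports: "Results from the experimental group were superior to those from the conventional physiotherapy group in all outcome measures".

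**The concern.** The hypothesis compares two exercise programmes, but the analysis sentence compares two time points. Improvement between a pre-operative assessment and week 8 would be expected under either programme, because the joint has been replaced and the patient has recovered in between. A significant within-arm change would therefore say nothing about bilateral against unilateral exercise.

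If the cohorts are compared, as the design text intends, several choices remain open: the model, the adjustment, the primary analysis set and the earlier patients who count as controls. The control data already exist, so these choices could be made after the answers are visible. In cohorts that were not randomised against each other, such choices can change the estimate.

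**Working it through.** **1. What the sample size implies.** Inputs from section 3: difference 2.27 s, SD 6.3 s, 80% power, 2:1 allocation. The two-sample formula for the smaller group is n = (1 + 1/2) × (z_α + z_β)² × SD² / difference², with SD²/difference² = 39.69/5.1529 = 7.70.

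- Two-sided 0.05: 1.5 × (1.960 + 0.842)² × 7.70 = 90.7, so 91 + 182 = 273.
- One-sided 0.05: 1.5 × (1.645 + 0.842)² × 7.70 = 71.4, so 72 + 144 = 216.

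The stated 216 comes from a two-group formula, which confirms that a between-cohort contrast is intended. It matches a one-sided level, not the stated two-sided one. That mismatch is a separate matter to reconcile and plays no part in this point.

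**2. What is fixed and what is not.**

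| Element | Where fixed |
|---|---|
| Outcome: TUG change from baseline | Section 2 |
| Time point: week 8 | Section 15 |
| Source of controls: the two feasibility studies | Text before section 2 |
| Direction: bilateral better than unilateral | Text before section 2 |
| Earlier arm that supplies the controls | Implied by the hypothesis, not stated |
| Between-cohort contrast in the analysis | Not in section 15 |
| Model and covariates | Nowhere |
| Primary set (intention-to-treat or per-protocol) | Nowhere |

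**3. Why adjustment needs a decision.** The earlier studies ran from December 2016 to March 2018. Their SWORD Phoenix patients lived outside the city limits, whereas this study takes patients within 30 km of the centre. Both cohorts contain hip and knee patients, and their proportions are not given.

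- *Joint mix.* If the hip share is p₁ here and p₀ among the controls, and mean TUG change differs by δ between hip and knee, the unadjusted comparison is off by (p₁ − p₀) × δ. The documents give none of these three values.
- *Baseline TUG.* Suppose this cohort starts D seconds slower, there is no true effect, and a difference of λD remains at week 8. Let b be the within-cohort slope of week-8 on baseline TUG. The change score is then off by −(1 − λ)D and the baseline-adjusted estimate by (λ − b)D. The first is unbiased when λ = 1 (the difference persists), the second when λ = b (it regresses). The two estimates always differ by (1 − b)D.

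**4. Illustration of that disagreement; every input except 6.3 s is assumed.** b = r × SD_f / 6.3, with D = 1 s.

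- r = 0.2, SD_f = 4 s: b = 0.13, difference 0.87 s.
- r = 0.6, SD_f = 6.3 s: b = 0.60, difference 0.40 s.
- r = 0.8, SD_f = 6.3 s: b = 0.80, difference 0.20 s.

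Per assumed second of imbalance, the two methods would differ by 0.20 to 0.87 s, which is 9% to 38% of 2.27 s. This shows only that the choice of method can matter. It does not estimate a bias in this trial.

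**The case against.** Section 15 can fairly be read as naming the outcome variable and time point, in line with section 2, and leaving the comparator to the design text and section 3. On that reading the contrast is not wrong, only incompletely described. This largely stands. A reader might infer that the study has abandoned its historical control for a before-and-after analysis, but the documents do not support that: the design text and section 3 both point to a between-cohort comparison. The charitable reading still leaves no model, adjustment, primary set or stated control arm.

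A reader might also infer that conventional-physiotherapy patients are to be counted among the controls. The documents do not say so. The hypothesis names the unilateral programme, which makes the earlier SWORD Phoenix arms the natural comparator, and 72 is a calculated requirement, not a selected set. What stands is that the exclusion is unwritten, while the sample-size inputs pool all 131 participants. Since the conventional group is reported to have done worse, including it would favour the bilateral programme.

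Finally, a reader might infer a known bias or false-positive rate. Neither follows, because the documents give no cohort imbalance, week-8 SD or correlation.

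**Conclusion.** The point holds as an omission at the centre of the analysis plan. Section 15 does not state the between-cohort comparison that the hypothesis needs. Followed literally, it gives a within-arm change that cannot test that hypothesis. Read with the rest of the protocol, it gives a change-score comparison of non-randomised cohorts of mixed joints, with no stated adjustment, primary set or restriction to the unilateral arms.

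This rests on the text alone. The size of any resulting bias is unknown, and its direction depends on cohort differences that the documents do not report. The comparator arm, contrast, model and primary set must be written down before the cohorts are compared. The model proposed below is one reasonable choice; the need to fix one in advance does not depend on it.

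**What to change.** Replace the last sentence of section 15 with wording such as:

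> The primary analysis compares TUG change from baseline to week 8 between this study and all patients in the unilateral SWORD Phoenix arms of the two feasibility studies. Patients who received conventional physiotherapy are not included. The analysis uses the intention-to-treat set and linear regression with cohort as factor, adjusted for joint (hip or knee) and pre-operative TUG, and reports the estimate with a 95% confidence interval.

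Also state that:

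- the joint-adjusted change-score comparison without baseline TUG is a prespecified sensitivity analysis, and both estimates are reported because they rest on different assumptions;
- the per-protocol analysis is supportive, and within-arm change is descriptive;
- HOOS, KOOS and range-of-motion comparisons are made within joint and are secondary or exploratory;
- adjustment does not remove differences in calendar time or residence.

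The section 2 outcome is unchanged. Joint and pre-operative TUG are already collected in this study, so no visit or measurement is added. The costs are a patient-level merge with the feasibility data and confirmation of how many unilateral controls exist, which the documents do not say. The two estimates may also disagree, and that would have to be reported as uncertainty. The significance level should follow from the separate reconciliation of 216 with two-sided 0.05.
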